### **9.6.3.1 Time from Randomization to the First Confirmed (adjudicated) Occurrence of Cardiovascular-Related Death, Non-fatal Myocardial Infarction or Non-fatal Stroke**

This endpoint is identical to the primary endpoint, only counting CV-related deaths, and not all-cause deaths as failures. Time, measured in days, from randomization to the first confirmed (adjudicated) occurrence of CV-related death, non-fatal myocardial infarction or non-fatal stroke, will be analyzed using the Kaplan-Meier estimator of the survival function and the log-rank test of the null hypothesis of equal hazard functions, stratified by age group and region. The p-value of the two-sided log-rank test with significance level of 5% will be presented along with plots of the estimated survival functions for the two treatment groups, stratified by age group and region. The treatment effect of degarelix will be further examined by fitting a stratified Cox regression model. The model will include treatment as a factor, be adjusted for the baseline CV risk factors and stratified by age-group and region. The 95% confidence limits and associated p-value for the hazard ratio comparing treatment with degarelix to leuprolide will be presented.

### **9.6.3.2 Time from Randomization to the First (adjudicated) Occurrence of the Individual Components of the MACE Composite Endpoint**

Time from randomization to the first adjudicated occurrence of the individual components of the MACE composite endpoint is defined as the number of days from randomization to the first adjudicated myocardial infarction / stroke. The occurrence of the components of the MACE composite endpoint will be adjudicated by the external independent CEC Committee. In order to correctly assess the treatment effect associated with degarelix with respect to the time to individual components of the MACE composite endpoint, it is necessary to account for the competing risk, death due to other causes. The above components of the MACE composite endpoint will be analyzed separately. The log-rank test stratified by age-group and region will be used to examine the null hypothesis of equal cumulative cause specific hazard functions. The p-value of the two-sided log rank test with significance level of 5% will be presented along with the plots of the estimated cumulative cause specific hazard functions for both treatments obtained from the Nelson-Aalen estimator, stratified by age group and region.

### **9.6.3.3 Time from Randomization to Confirmed (adjudicated) Cardiovascular-Related Death**

Time from randomization to CV-related death is defined as the number of days from randomization to adjudicated CV-related death. Cause of death will be adjudicated by the external independent CEC Committee. Undetermined death will be presumed and analyzed as non-CV-related deaths on the secondary analysis. The time measured in days, from randomization to adjudicated CV-related death, will be analyzed as outlined in Section 9.6.3.2.

### **9.6.3.4 Time from Randomization to the First Confirmed (adjudicated) Unstable Angina Requiring Hospitalization**

Time, measured in days, from randomization to first adjudicated hospitalization for unstable angina will be analyzed as the individual components of the MACE primary endpoint, as outlined in Section 9.6.3.2.

### **9.6.3.5 Time from Randomization to Death Due to Any Cause**

Time from randomization to death due to any cause (overall survival) is defined as the number of days from randomization to death. The time measured in days, from randomization to death due to any cause, will be analyzed using the Kaplan-Meier estimator of the survival function and the log-rank test of the null hypothesis of equal hazard functions, stratified by age group and region. The p-value of the two-sided log-rank test with significance level of 5% will be presented along with plots of the estimated survival functions for the two treatment groups, stratified by age group and region. The treatment effect of degarelix will be further examined by fitting a stratified Cox regression model for the time to death from any cause. The model will include treatment as a factor, be adjusted for the baseline CVD risk factors as appropriate and stratified by age group and region. The 95% confidence limits and associated p-values for the hazard ratio comparing treatment with degarelix to leuprolide will be presented.

### **9.6.3.6 Testosterone Levels at Days 28, 168 and 336 in the Degarelix and Leuprolide Treatment Groups**

The proportion of patients with testosterone levels  $\leq 0.5$  ng/mL at each time point (Days 28, 168 and 336), as well as the proportion of patients with testosterone levels  $\leq 0.5$  ng/mL between Days 28 and 168 and Days 28 and 336, will be presented descriptively.

### **9.6.3.7 Time from Randomization to Failure in Progression-Free Survival**

Progression-free survival is a composite endpoint consisting of the following conditions:

- Radiographic disease progression defined as one or more new metastatic skeletal lesions observed on bone scan; one or more new metastatic extra-skeletal lesions at least 1.5 cm in greatest dimension visible on CT or MRI scan as confirmed by the Investigator.
- Introduction of additional therapy related to prostate cancer treatment including radiation, anti-androgens (except for initial flare protection) and second-line treatment.

- PSA failure defined as an increase in serum PSA of 50%, and at least 5 ng/mL, compared to nadir, measured on two consecutive occasions at least 2 weeks apart.
- Death.

Time to PFS failure is therefore defined as the time, measured in days, from randomization to the first occurrence of one of the above composite endpoint criteria. Time to PFS failure will be analyzed using the Kaplan-Meier estimator of the survival function and the log-rank test of the null hypothesis of equal hazard functions. The p-value of the two-sided log-rank test with significance level of 5% will be presented along with plots of the estimated survival functions for the two treatment groups.

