##### *Prostate Cancer-Related Objectives*

- To monitor testosterone levels at Days 28, 168, and 336 in the degarelix and leuprolide treatment groups
- To evaluate the progression-free survival (PFS) failure rates (defined as either death, radiographic disease progressiona, introduction of additional therapy related to prostate cancerb or PSA failurec, whichever is first) in the degarelix and leuprolide treatment groups
  - a. One or more new metastatic skeletal lesions observed on bone scan; one or more new metastatic extra-skeletal lesions at least 1.5 cm in greatest dimension visible on computed tomography (CT) or magnetic resonance imaging (MRI) scan as confirmed by the Investigator.
  - b. Additional therapy includes radiation, anti-androgens (except for initial symptomatic flare protection) and second-line treatment.
  - c. PSA failure is defined as an increase in serum PSA of 50%, and at least 5 ng/mL, compared to nadir, measured on two consecutive occasions at least 2 weeks apart.
- To compare the effects of degarelix with leuprolide with regards to local urinary tract and prostate cancer-related symptoms with the International Prostate Symptom Score (IPSS) questionnaire

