## 4 SELECTION OF TRIAL POPULATION

### 4.1 Trial Population

#### 4.1.1 Inclusion Criteria

Each patient must meet the following inclusion criteria before entry into the trial:

1. Signed informed consent obtained before any trial-related activity is performed.
2. Histologically confirmed adenocarcinoma of the prostate.
3. Clinical tumor staging (Tumor, Nodule and Metastasis [TNM]) available prior to treatment start; radiographic imaging (bone scan and/or CT scan and/or MRI) performed within 3 months prior to randomization. If no radiographic image is available at the time of screening, a bone scan should be performed.
4. Investigator judgment to initiate continued ADT with an intended treatment duration of 12 months or longer including any of the following disease categories:
  - A. Patients with metastatic prostate cancer at the time of diagnosis.
  - B. Patients with prostate cancer who develop metastases after local therapy.
  - C. Patients with prostate cancer with very high-risk, high-risk or intermediate-risk disease with features of unfavourable prognosis who are going to be treated with definitive radiation therapy in combination with at least 12 months of neoadjuvant/adjuvant ADT.
  - D. Patients with biochemical recurrence after local therapy who have a PSA doubling time <12 months.
  - E. Patients previously treated with definitive local therapy (without ADT combination) who due to risk features such as positive margins, seminal vesicle invasion, extracapsular extension, or detectable PSA, will be treated with salvage radiation therapy in combination with neoadjuvant/adjuvant ADT that is planned for 12 months or longer.
  - F. Patients with locally advanced prostate cancer who are not candidates (who are unsuited) for definitive therapy with surgery or radiation and will be treated with primary ADT.
5. Patients must be treatment-naïve with regard to ADT at time of randomization (with the exception of prior history of neoadjuvant/adjuvant ADT to definitive therapy for which the last administration, e.g., injection of a depot ADT formulation was at least 12 months prior to randomization).
6. Patients must have a screening serum testosterone level above the lower limit of normal range, defined as >150 ng/dL (5.2 nmol/L), apart from those who had prior neoadjuvant/adjuvant ADT (>12 months prior to randomization) where non-castrate range (>50 ng/dL or  $\geq 1.73$  nmol/L) should be applied.

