#### **4.3 Restrictions**

##### **4.3.1 Prior and Concomitant Therapies**

Patients must be treatment-naïve with regard to ADT at time of randomization, except for neoadjuvant/adjuvant ADT given in combination with prostatectomy or radiotherapy with curative intent. This treatment should have been terminated at least 12 months prior to randomization.

Concomitant treatment with anti-androgens (e.g. bicalutamide 50 mg once a day) for a maximum period of up to 28 days is allowed in metastatic patients requiring initial symptomatic flare protection at the discretion of the Investigator. Other hormonal management of prostate cancer is not allowed prior to or during the trial (Section 4.1). However, if a patient develops signs of disease progression, e.g. increased clinical signs and symptoms or rising PSA, additional secondary therapy can be added at the discretion of the Investigator to treat the prostate cancer. Patients on secondary treatments will be handled as described in Section 4.3.2.

The Investigator will be encouraged to treat patients for their pre-existing CVD and any CVD that may be diagnosed during the trial according to standard-of-care. Other medication, which is considered necessary for the patient's safety and well-being, may be given at the discretion of the Investigator.

Details of all concomitant medications, and other therapies including surgical procedures, e.g. revascularizations including the main reason for their prescription must be recorded in the medical source data and the eCRF for all eligible patients at the Screening visit. This information should include name of the drug, route of administration, indication, and duration of treatment. It has to be clearly stated if the medication is given to treat progression of the prostate cancer. Any changes (including new therapies) must be recorded at each subsequent trial visit.

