9.3.6 Time from Randomization to Failure in Progression-Free Survival

Progression-free survival (PFS) is a composite endpoint consisting of the following conditions:

- Death
- Radiographic disease progression defined as one or more new metastatic skeletal lesions observed on bone scan; one or more new metastatic extra-skeletal lesions at least 1.5 cm in greatest dimension visible on computed tomography or magnetic resonance imaging scan as confirmed by the Investigator.
- Introduction of additional therapy related to prostate cancer treatment including radiation, anti-androgens and second-line treatment. (ATC and MedDRA codes for disease progression are included in Appendix 3)
- PSA failure defined as the time from randomization to the second occasion (must be at least two weeks apart from the first and correspond to consecutive measurements) in which the PSA value fulfills the following criteria:
 - I. An absolute increase of ≥ 5 ng/ml above nadir and
 - II. An increase of > 50 % of nadir

Time to PFS failure is therefore defined as the time, measured in days, from randomization to the first occurrence of one of the above composite endpoint criteria. Patients discontinuing from treatment/withdrawn from the study will be censored at the time of discontinuation/withdrawal. Time to PFS failure will be analyzed using the Kaplan-Meier estimator of the survival function, the Cox regression model for the hazard rate and the log-rank test of the null hypothesis of equal hazard functions, stratified by age group and region. The p-value of the two-sided stratified log-rank test with significance level of 5% will be presented along with plots of the estimated survival functions for the two treatment groups, stratified by age group and region. The estimated hazard ratio and the associated 95% confidence interval and p-value comparing the treatment with Degarelix to Leuprolide will also be presented.

TLF Table: Secondary Endpoint: Time to PFS Failure - FAS

TLF Figure: Survivor Function for Time to PFS Failure - FAS

Page 30 of 51

9.3.7 Testosterone levels at day 28, 168 and 336 in patients treated with degarelix and leuprolide

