Appendix 3 ATC codes and MedDRA terms for disease progression

A list of ATC codes for antiandrogens and additional therapies classified as disease progression are defined below. Please note that the list may be non-extensive.

Table 6 ATC Codes for Antiandrogens

Level 5 codes
L02BB01 Flutamide
L02BB02Nilutamide
L02BB03Bicalutamide
L02BB04Enzalutamide
G03HA01 Cyproterone

Table 7 ATC codes for Additional Therapy

Level 5 codes
L01DB07Mitoxantrone
L01CD02Docetaxel
L01XX11 Estramustine
L01CD01 Paclitaxel
L02AA01 Diethylstilbestrol
L02AA02 Polyestradiol phosphate
L02AA03 Ethinylestradiol
L02AA04 Fosfestrol
L02AB01 Megestrol
L02BG01 Aminoglutethimide
L02BX03 Abiraterone
G01AF11 Ketoconazole

Investigators recording of disease progression are marked as a tick-box on the Adverse Event form in the eCRF. The MedDRA terms to be used for radiation and second line treatment are defined below.

Page 47 of 51

Table 8 MedDRA Codes (preferred terms) for Radiation

10006089	Brachytherapy to prostate	PT
10014442	Electron radiation therapy to prostate	PT
10017683	Gamma radiation therapy to prostate	PT
10034955	Photon radiation therapy to prostate	PT
10061544	Radiotherapy to prostate	PT
10048205	X-ray therapy to prostate	PT
10014435	Electron radiation therapy to bone	PT
10017675	Gamma radiation therapy to bone	PT
10034947	Photon radiation therapy to bone	PT
10062089	Radiotherapy to bone	PT
10048197	X-ray therapy to bone	PT

 Table 9
 MedDRA Codes (preferred terms) for Second Line Treatment

10061916	Prostatectomy	PT
10050756	Radical prostatectomy	PT
10038961	Retro-pubic prostatectomy	PT
10042594	Supra pubic prostatectomy	PT
10044445	Transurethral prostatectomy	PT

The following terms are also to be classified as investigators recording of disease progression, in case the investigator did not check the tick-box, but only recorded the AE.

Table 10 MedDRA Codes (preferred terms) for additional classification of investigators recording of disease progression

10010264	Condition a ggravated	PT
10061818	Disea se progression	PT
10061819	Disea se recurrence	PT
10048669	Terminal state	PT
10051398	Malignant neoplasm progression	PT
10027452	Meta stases to bone	PT
10027459	Meta stases to lymph nodes	PT
10027457	Meta stases to liver	PT
10027458	Meta stases to lung	PT
10027463	Meta stases to pleura	PT
10062194	Metastasis	PT

Page 48 of 51

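### As written, the PFS endpoint does not exempt radiotherapy already planned at randomization under criteria 4C and 4E, so planned treatment can be scored as failure

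*Protocol*

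**What the plan says.** **Endpoint rule.** Protocol 9.6.3.7 lists as a PFS failure "Introduction of additional therapy related to prostate cancer treatment including radiation, anti-androgens (except for initial flare protection) and second-line treatment". Footnote b to the PFS objective (Protocol synopsis, Protocol 2.1.2 and SAP 2.1.2) has the same content: "Additional therapy includes radiation, anti-androgens (except for initial symptomatic flare protection) and second-line treatment". SAP 9.3.6 has "Introduction of additional therapy related to prostate cancer treatment including radiation, anti-androgens and second-line treatment", with no exception at all. PFS time runs from randomization to whichever component comes first.

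**Coding rule.** SAP Appendix 3 covers therapies classified as disease progression. It says "The MedDRA terms to be used for radiation and second line treatment are defined below", and Table 8 then lists prostate and bone radiation terms, among them "Radiotherapy to prostate" and a brachytherapy term. No condition on eligibility category, intent or start date is attached.

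**Eligibility.** Inclusion criterion 4 (Protocol 4.1.1) has six disease categories. Category 4C is for patients "who are going to be treated with definitive radiation therapy in combination with at least 12 months of neoadjuvant/adjuvant ADT". Category 4E is for patients treated earlier with local therapy who "will be treated with salvage radiation therapy in combination with neoadjuvant/adjuvant ADT that is planned for 12 months or longer".

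**Status.** Protocol 9.6.3 and SAP 9.3 place PFS among the other secondary endpoints, outside the fixed testing sequence and without multiplicity control.

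**The concern.** For two of the six categories, radiotherapy is part of the treatment plan at entry. A time-to-first-event rule that counts radiation without an exemption can turn that plan into the event. A 4C patient who starts prostate radiotherapy on, say, Day 60 would be a PFS failure on Day 60, whatever his cancer is doing. He then leaves the risk set, and a real progression later in the year is not counted.

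The stated objective is to evaluate PFS failure rates in each group. In these patients the endpoint would partly record when radiotherapy was scheduled. Such events should be about equally common in the two arms. They therefore raise both failure rates and pull the hazard ratio towards 1, which could mask a difference in cancer control in either direction.

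**Working it through.** **Reading the rules together**

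1. *Is planned radiotherapy exempted?* No. The Protocol writes out one exception, for flare-protection anti-androgens. SAP 2.1.2 repeats it and SAP 9.3.6 drops it. Neither document defines additional therapy as therapy beyond the entry plan.
2. *Would censoring remove the event?* No. SAP 9.3.6 censors PFS at treatment discontinuation or study withdrawal. The general rule in SAP 9.1 adds prohibited hormonal therapies, and radiotherapy is not among those (Protocol 4.3.2, SAP Appendix 4).
3. *Would true progression usually be seen first?* Probably not. The only scheduled post-baseline bone scan is at End-of-Treatment or End-of-Trial. PSA is drawn every 3 months, and PSA failure needs two consecutive qualifying values (Protocol 7.2.1.2, 9.6.3.7).
4. *Which planned radiotherapy is captured?* Only that started after randomization and coded to Table 8. Prostate radiotherapy in 4C clearly fits. For 4E, salvage treatment may follow surgery, and the documents do not settle whether it would be coded to a prostate term.

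**Size (illustration only)**

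The plan has no PFS event rate, PFS power or 4C/4E share, so there is no figure to reproduce. Assumed inputs:

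- f, the share of patients whose planned radiotherapy is scored as an event, equal in both arms: 10% to 50%.
- p, the true 336-day failure risk on leuprolide: 10%, 20% or 30%.
- True hazard ratio: 0.70, so degarelix risk = 1 − (1 − p)^0.70, which is 7.1%, 14.5% and 22.1%.

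Observed failure in an arm = f + (1 − f) × (true risk). Observed ratio = ln(1 − observed degarelix failure) / ln(1 − observed leuprolide failure). This is a ratio of cumulative hazards at Day 336. It equals the hazard ratio under constant hazards, where it is (r + 0.70·l)/(r + l) with r = −ln(1 − f) and l = −ln(1 − p).

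Worked case, p = 10% and f = 10%: leuprolide 0.10 + 0.90 × 0.10 = 0.190; degarelix 0.10 + 0.90 × 0.071 = 0.164; ratio = ln(0.836)/ln(0.810) = 0.85.

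Each cell gives the observed ratio, with observed leuprolide failure in brackets:

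| True leuprolide failure | f = 10% | f = 20% | f = 30% | f = 50% |
|---|---|---|---|---|
| 10% | 0.85 (19%) | 0.90 (28%) | 0.93 (37%) | 0.96 (55%) |
| 20% | 0.80 (28%) | 0.85 (36%) | 0.88 (44%) | 0.93 (60%) |
| 30% | 0.77 (37%) | 0.82 (44%) | 0.85 (51%) | 0.90 (65%) |

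*Event mix*, using the 545 randomized patients in SAP section 3 and taking planned radiotherapy as the first event in every such patient. At p = 20% and f = 30%, planned-radiotherapy events = 545 × 0.30 ≈ 164. True events = 0.70 × 272.5 × (0.200 + 0.145) ≈ 66. So 164/(164 + 66) ≈ 71% of scored events would be planned treatment. At f = 10% the figures are 54 and 85, or 39%.

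**The case against.** **The intended meaning may be narrower.** Protocol 4.3.1 speaks of additional secondary therapy for patients who show signs of progression. Appendix 3 is headed as concerning disease progression and mentions a progression tick-box on the adverse event form just before the radiation terms. Protocol 8.2.2 records relation to progression for each adverse event. A reader could take additional therapy to mean therapy beyond the entry plan. That may well be the intent, but neither document states it. The SAP ties the tick-box to the Table 10 terms, not to Table 8, and Protocol 8.2.2 says a procedure is not itself an adverse event. A programmer following SAP 9.3.6 and Table 8 would count planned prostate radiotherapy.

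**Randomization balances the planned radiotherapy.** This stands against any claim that one arm is favoured. It does not protect the absolute failure rates or prevent dilution.

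**Stronger readings a reader might infer.**

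- *Any radiation counts.* The operational list is limited to prostate and bone terms. The caveat that the lists may be incomplete is written about the ATC codes.
- *All planned treatment in 4C and 4E is certain to be scored.* Start date and coding decide that, especially in 4E.
- *The trial's main conclusions are at risk.* PFS lies outside the hierarchy and did not drive the sample size. Radiotherapy does not trigger censoring of MACE.
- *The dilution is known to be severe.* A low true failure rate maximises it, and the documents supply no rate.

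**Conclusion.** The concern holds as a fault in the written rule. The PFS definition and Table 8 do not exempt radiotherapy that 4C and 4E patients were enrolled to receive, so that treatment is scored as failure when it starts after randomization and is coded to a listed term.

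The direction is clear if planned radiotherapy is about equally common in both arms: higher failure rates in both, later progression uncounted, hazard ratio nearer 1. The size is not known. Over the assumed ranges a true ratio of 0.70 would appear as about 0.77 to 0.96. This rests on an invented true ratio, failure rate and radiotherapy share, and on every planned course in that share being captured.

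Severity is moderate. The primary MACE analysis, the key secondary sequence and the 66-event, 876-patient calculation are unaffected.

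**What to change.** In the Protocol synopsis, Protocol 2.1.2 footnote b, Protocol 9.6.3.7, SAP 2.1.2 footnote b, SAP 9.3.6 and SAP Appendix 3 Table 8, replace radiation with: *radiation other than the definitive or salvage radiotherapy planned at randomization under criterion 4C or 4E*. All six places need it, or the documents will contradict each other.

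In 4C and 4E patients, count a Table 8 prostate term only if the recorded reason for the therapy is progression. Bone-radiation terms still count.

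**Cost.** Wording changes and one programming filter, plus retrieval of two items per patient: the eligibility sub-category and the reason for the radiotherapy. Possible sources are the eligibility documentation, prostate cancer history and concomitant therapy records (Protocol 4.3.1, 10.1). Protocol 4.3.1 asks for the main reason for concomitant therapies. Its specific sentence, "It has to be clearly stated if the medication is given to treat progression of the prostate cancer", refers to medication and does not clearly reach radiotherapy. The documents do not confirm that the sub-category is an eCRF field, so a check of source records may be needed.
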